9.2. Severity

The term “severe” is used to describe the intensity (severity) of a specific event (as in mild, moderate, or severe myocardial infarction). Even though the event itself may be of relatively minor medical significance (such as a severe headache), this is not the same as “serious,” which is based on subject/event outcome or action criteria as described above and are usually associated with events that pose a threat to a subject’s life or functioning. A severe adverse event is not necessarily serious. For example, persistent nausea of several hours duration may be considered severe nausea but not meet the definition of a SAE. On the other hand, a stroke resulting in only a minor degree of persistent disability may be considered mild, but would be defined as a SAE based on the above noted criteria. Seriousness (not severity) serves as a guide for defining regulatory reporting obligations.

For both serious and non-serious adverse events, the Investigator must determine the severity of the event using the following definitions:

Mild The event does not interfere in a significant manner with the subject’s normal functioning level. It may be an annoyance but does not cause any limitation in usual activity.

Moderate The event produces some impairment of functioning but is not hazardous to health. It is uncomfortable or an embarrassment and may cause some limitation in usual activity.

Severe The event produces significant impairment or incapacitation and is a definite hazard to the subject's health.

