10.7.5 Safety Analyses

Safety assessments will be based on the incidence, severity, and type of adverse events, and clinically significant changes in the subject's clinical laboratory tests, vital signs, ECGs and physical examinations.

Adverse events will be coded using the MedDRA adverse event coding system for purposes of summarization. All adverse events reported will be listed in the data listings. Treatment emergent adverse events (TEAEs) will be tabulated for each treatment cohort and overall, where treatment emergent is defined as any adverse event which occurs after administration of the first dose of study drug and up through the final visit (Visit 3 for subjects from TEN-01-302 and Visit 4 for subjects from TEN-01-301), any event that is considered drug-related regardless of the start date of the event, or any event that is present at baseline but worsens in severity or is subsequently considered drug-related by the investigator. TEAEs will also be tabulated by whether events are considered related to treatment (possibly or probably drug-related, or unknown in relationship) and by severity. Serious adverse events and TEAEs resulting in study discontinuation will be tabulated.

Actual values and change from baseline values for clinical laboratory tests (including urinalysis) will be summarized at each visit collected during the study for each treatment cohort and overall. The frequency of clinically significant abnormal laboratory test values will be tabulated by treatment cohort and overall. Shift tables will be derived for changes in laboratory tests from the last values obtained during TEN-01-301 or TEN-01-302 to Visit 3 or 4.

Vital signs will be summarized descriptively for actual values and change from baseline values by visit and treatment cohort as well as overall. Vital signs are collected at study visits 2, 3 and 4, as applicable. Baseline for the vital signs will be the last values obtained during TEN-01-301 or TEN-01-302.

12-lead electrocardiogram (ECG) results will be summarized descriptively for actual values and change from baseline values by treatment cohort and overall for each visit (Visit 3 or Visit 4 as applicable). Baseline for the ECG will be the last values obtained during TEN-01-301 or TEN-01-302. The overall interpretation will be

summarized with number of subjects and percentages for the normal and abnormal ECG result categories.

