3.7 Safety Analyses

Safety assessments will be based on the incidence, severity, and type of adverse events, and clinically significant changes in the subject's clinical laboratory tests, vital signs, ECGs, and physical examinations.

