3.7.1 Adverse Events

Adverse events will be coded using the MedDRA adverse event coding system for purposes of summarization. All adverse events reported will be listed in the data listings. Treatment emergent adverse events (TEAEs) will be tabulated for each treatment cohort and overall. A treatment-emergent AE (TEAE) is any AE that starts on or after the first dose of study drug through the final visit (Visit 3 for subjects from TEN-01-302 and Visit 4 for subjects from TEN-01-301), any event that is considered drug related regardless of the start date, or any event which occurs prior to the first dose of study drug and worsens in severity or is

subsequently considered drug-related by the investigator. An AE is considered drug related if it is possibly related or probably related to study drug.

TEAEs will also be tabulated by whether events are considered related to treatment and by severe severity. Serious adverse events (SAEs) and TEAEs resulting in study discontinuation will be tabulated.

Summarization of AEs will include subject incidence of the following:

- All TEAEs
- Drug-related TEAEs
- Severe TEAEs
- Severe and drug-related TEAEs
- SAEs
- Drug-related SAEs
- Death due to AEs
- TEAEs leading to study drug discontinuation
- Drug-related TEAEs leading to study drug discontinuation

An overall summary table will contain the number and percentage of subjects ever having one of the above listed subsets of AEs. All TEAEs will be summarized for each treatment cohort and overall by MedDRA system organ class (SOC), by SOC and preferred term (PT), and by PT with the number and percentage of subjects. If a subject has more than 1 occurrence of the same TEAE, he/she will be counted only once within that preferred term and system organ class in the summary tables. The most severe occurrence of a repeat TEAE, as well as the closest relationship of the TEAE to the study drug will be used for the analyses.

TEAEs related to study drug, severe TEAEs, SAEs, and TEAEs leading to study drug discontinuation will be summarized in the same manner. That is, summaries will be provided for the numbers and percentages of subjects by SOC, SOC and PT, and PT.

All AEs will be included in by-subject listings. Specific by-subject listings of SAEs and TEAEs leading to study drug discontinuation will be provided. The number of days between first dose and when the event occurred will be presented in listings as well (i.e., relative study day), as will duration of the AE.

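### SAP 3.7.1 narrows the protocol's tabulation of TEAEs by severity to severe events only, without saying so, so the tables it names cannot separate mild from moderate events

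*SAP*

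**What the plan says.** Protocol 9.2 sets a three-grade scale and makes grading compulsory: "For both serious and non-serious adverse events, the Investigator must determine the severity of the event using the following definitions". A mild event leaves usual activity unrestricted. Of a moderate event the protocol says "The event produces some impairment of functioning but is not hazardous to health", and adds that it may restrict usual activity to some degree. A severe event is incapacitating or significantly impairing, and a definite health hazard.

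Protocol 10.7.5 then plans the output: "TEAEs will also be tabulated by whether events are considered related to treatment (possibly or probably drug-related, or unknown in relationship) and by severity". It does not restrict this to one grade.

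SAP 3.7 opens the safety section in the same spirit: "Safety assessments will be based on the incidence, severity, and type of adverse events", followed by laboratory tests, vital signs, ECGs and physical examinations. SAP 3.7.1 then specifies "TEAEs will also be tabulated by whether events are considered related to treatment and by severe severity". Its list of subject-incidence summaries has nine items. The only two that use severity are severe TEAEs and "Severe and drug-related TEAEs". For the SOC/PT tables, beyond the one for all TEAEs, it says "TEAEs related to study drug, severe TEAEs, SAEs, and TEAEs leading to study drug discontinuation will be summarized in the same manner". Where a subject has repeats of the same TEAE, the worst occurrence is used. All adverse events go into by-subject listings.

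Protocol Section 10 lets the SAP change the statistical plan without a protocol amendment, provided the SAP addresses the change.

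**The concern.** The protocol promises a tabulation across the severity scale, and the SAP delivers one grade of it. The SAP text neither flags nor explains the narrowing, so someone reading the two documents together cannot tell whether it was intended.

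Safety is the study's only objective, and no statistical testing is planned, so the descriptive tables are its main output. Protocol 8.2.1 says the study should help describe safety and tolerability at this dose. For long-term tolerability, the boundary between mild and moderate is informative, because the protocol draws it at whether an event may interfere with ordinary activity. If the summary tables separate only severe from everything else, they cannot show how the non-severe events divide across that boundary.

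**Working it through.** The plan states no figure on this point, so the check is a comparison of text followed by a short argument about what the named tables can identify.

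**Step 1: the severity outputs, side by side**

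| Element | Protocol | SAP |
|---|---|---|
| Grades collected | Mild, moderate, severe, for every event (9.2) | Not changed |
| Severity as a basis of the safety assessment | Yes (10.7.5) | Yes (3.7) |
| Tabulation of TEAEs by severity | Yes, no restriction (10.7.5) | Severe only (3.7.1) |
| Items in the summary list that use severity | No such list | 2 of 9, both severe (3.7.1) |
| SOC/PT tables | Not itemised | All, related, severe, serious, leading to discontinuation (3.7.1) |
| Statement that this differs from the protocol | Changes to Section 10 are to be addressed in the SAP | None in the text provided |

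**Step 2: is it a slip of wording?** The phrase about severe severity is awkward and could be read as a typing error for severity. That is unlikely. The summary list and the SOC/PT paragraph make the same restriction independently, so three places in SAP 3.7.1 agree.

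**Step 3: can the missing split be derived from the named tables?** For any PT, SOC or cohort, let

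- A = subjects with any TEAE (all-TEAE table),
- S = subjects with a severe TEAE (severe-TEAE table),
- M = subjects whose worst grade is moderate,
- L = subjects whose worst grade is mild.

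Then A = L + M + S, so L + M = A − S. That is one equation in two unknowns, and M may lie anywhere in 0 ≤ M ≤ A − S.

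Illustration with assumed counts, which are not from the documents: A = 60 and S = 6 give L + M = 60 − 6 = 54. M is then any whole number from 0 to 54.

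**Step 4: do the other tables help?** No. The related, serious and discontinuation tables each count a subset of subjects or events, and none is split between mild and moderate. Seriousness is no substitute for severity, as Protocol 9.2 itself explains.

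**Step 5: is the missing table feasible?** Yes. The grade is recorded for every event, and the worst-occurrence rule in SAP 3.7.1 already assigns one grade per subject for a repeated event. The layout needs 3 grades × (5 cohorts + 1 overall) = 18 columns.

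**The case against.** The strongest case against runs as follows.

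- **The protocol permits the change.** Section 10 leaves the methods to the SAP and asks for no separate list of changes. The SAP states its severity outputs openly and consistently. This stands to the extent that the narrowing is not forbidden. What remains is that the SAP neither identifies it as a change nor gives a reason, while SAP 3.7 still names severity in general.
- **The full table list is elsewhere.** SAP Section 4 places it in a stand-alone programming document that is not available here. A reader might infer that no table in the study report will show mild and moderate separately. The documents do not support that; only the tables named in the SAP text can be judged. If the separate list does contain such a table, SAP 3.7.1 should be brought into line with it.
- **The information exists.** A reader might infer that the study cannot distinguish mild from moderate events at all. It can: the grades are collected and all adverse events are listed by subject, although the SAP does not name the listing columns. The loss is one of summary. With about 300 subjects planned, listings do not replace a tabulation.
- **The clinical contrast can be overstated.** Moderate events may limit activity; the protocol does not say they always do. Nor is severity part of the primary objective as worded. It is one of three descriptors of adverse events among several kinds of safety data.
- **The worst-occurrence rule proves nothing.** The severe tables also need a rule for repeats, so its presence does not show that a full table was intended. Agreed; it matters only because it makes the fix easy.
- **Little turns on it.** No endpoint or decision rule depends on mild versus moderate, and 18 columns for about 300 subjects will leave some cells sparse. This is fair, and it is why the point ranks low.

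**Conclusion.** The point holds in limited form. The protocol plans a tabulation "possibly or probably drug-related, or unknown in relationship) and by severity"; the SAP keeps only the severe grade and does not identify this as a change. In every table the SAP text names, mild and moderate are merged, and the moderate count is bounded only by 0 and A − S.

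The size cannot be expressed as a share of events, because the documents give no expected split by severity. The conclusion does not depend on one.

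It rests on two assumptions: that the restriction is meant as written, which the agreement of three places in SAP 3.7.1 supports, and that the separate programming document does not already add the missing table, which cannot be checked. The consequence is an incomplete summary of one stated basis of the safety assessment. No data are lost, and no planned result is invalidated. It is a correction worth making, of low priority.

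**What to change.** In SAP 3.7.1, restore the protocol's tabulation: one table of TEAEs by SOC and PT and by maximum severity (mild, moderate, severe), for each cohort and overall, with each subject counted once per term under the existing worst-occurrence rule. Keep the severe-TEAE tables, and make the programming specification agree.

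If the restriction to severe events is deliberate, the lesser remedy is a sentence in the SAP identifying it as a change from Protocol 10.7.5 and giving the reason. That would settle the mismatch but would not supply the summary.

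The cost is one longer table, 18 columns wide if all grades and groups sit side by side, with some sparse cells in the smaller cohorts. It needs no new data collection and, under Protocol Section 10, no protocol amendment.

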3.7.2 Clinical Laboratory Tests

The list of clinical laboratory tests collected during this study is presented in Appendix A of the protocol. Serum chemistry, hematology, and urinalysis results will be summarized with descriptive statistics at Enrollment (based on the last values obtained during TEN-01-301 or TEN-01-302), and Visit 3 (for subjects enrolled from TEN-01-302) or Visit 4 (for subjects enrolled from TEN-01-301) by treatment cohort and overall. For continuous tests, actual values and change from enrollment will be summarized. For categorical tests, the number and percentage of subjects in each category will be presented for each visit. Serum chemistry tests included in these summaries will be albumin, alkaline phosphatase, ALT, AST,

bicarb/CO₂, total bilirubin, direct bilirubin, indirect bilirubin, calcium, chloride, total cholesterol, creatinine, glucose, inorganic phosphorous, LDH, potassium, total protein, sodium, triglycerides, BUN/urea, and uric acid. Hematology tests included in these summaries will be WBC, RBC, MCV, MCH, MCHC, hemoglobin, hematocrit, and platelet count. Differentials consisting of bands, monophils, neutrophils, eosinophils, lymphocytes, and basophils will be included in the listings only. Urinalysis tests included in these summaries will be appearance, specific gravity, and pH. Protein, glucose, ketones, blood, nitrite, and microscopic results will be presented in listings only.

The frequency of clinically significant abnormal laboratory test values will be tabulated by treatment cohort and overall.

Shift tables classifying normal range results (low out of normal range, normal, or high out of normal range) between enrollment and the final visit will be tabulated by treatment cohort and overall. Missing results for each pairwise summary will be tabulated.

Data listings of clinical laboratory tests will include flags for abnormal results.

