8.1. Evaluations and procedures at Visit 1 (Day 1)

The following procedures will be conducted at Visit 1:

- Informed Consent
- Inclusion/Exclusion Criteria
- Drug Dispensed

8.1.1 Telephone contacts (Weeks 5±1, 9±1, 17±1, 22±1, for subjects from TEN-01-301 also Weeks 30±1 and 35±1)

- Concurrent Medications (changes since last visit)
- Adverse Events

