2. STUDY CHARACTERISTICS

2.1 Primary Objective

The primary objective of this study is to assess the safety of tenapanor 50 mg for the treatment of constipation-predominant irritable bowel syndrome (IBS-C) when administered twice daily (BID) for up to 52 weeks.

This SAP will address the primary objective for this study. If other objectives are identified or the usage of the data collected for the purposes of this study change, these objectives will be addressed at a later time through a separate analysis plan and/or report.

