3.6 Statistical Analyses

Summary tabulations will be presented which will display descriptive statistics by visit for five treatment cohorts and for all subjects in the safety analysis set. These treatment cohorts are identified below.

Treatment Cohorts for Summary Tabulations

Cohort	Protocol 301		Protocol 303
	12-Weeks	4-Weeks	39-Weeks
1	Tenapanor 50 mg BID	Tenapanor 50 mg BID	Tenapanor 50 mg BID
2	Tenapanor 50 mg BID	Placebo	Tenapanor 50 mg BID
3	Placebo	Tenapanor 50 mg BID	Tenapanor 50 mg BID
	Protocol 302		
	26-Weeks		26-Weeks
4	Tenapanor 50 mg BID		Tenapanor 50 mg BID
5	Placebo		Tenapanor 50 mg BID

The number of observations, mean, standard deviation, minimum, median, and maximum values will be displayed for continuous variables, and the number and percent of subjects per category will be displayed for categorical data.

As this is an open label study of only treatment with tenapanor 50 mg BID, no statistical testing will be performed.

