3.7.3 Vital Signs and 12-lead Electrocardiogram

Vital signs (body weight, heart rate, respiratory rate, sitting systolic blood pressure, sitting diastolic blood pressure, and temperature) will be summarized descriptively for actual values and change from enrollment values by treatment cohort and overall by visit. Enrollment values for the vital signs will be the last values obtained during TEN-01-301 or TEN-01-302.

Electrocardiogram results (heart rate, PR interval, QRS duration, QT, QTcB and QTcF intervals) will be summarized descriptively for actual values and change from enrollment values by treatment cohort, overall, and visit. Enrollment values will be obtained in a similar manner as for the vital signs. The overall interpretation will be summarized with number of subjects and percentages for the normal and abnormal ECG result categories.

All vital signs and electrocardiogram results will be listed. Abnormal or clinically significant results will be flagged.

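### Change and lab-shift tables start from the last parent-study value; if that is an end-of-study value, none shows within-subject change over 52 weeks for Cohorts 1 and 4

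*SAP*

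**What the plan says.** SAP 3.7.2 summarizes chemistry, hematology and urinalysis "at Enrollment (based on the last values obtained during TEN-01-301 or TEN-01-302") and again at the subject's final visit. Continuous tests get actual values and change from enrollment; shift tables run from enrollment to the final visit. SAP 3.7.3 follows the same rule: "Enrollment values for the vital signs will be the last values obtained during TEN-01-301 or TEN-01-302", with ECG handled similarly.

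Protocol 10.7.5 agrees. For laboratory shifts: "Shift tables will be derived for changes in laboratory tests from the last values obtained during TEN-01-301 or TEN-01-302 to Visit 3 or 4". For ECG: "Baseline for the ECG will be the last values obtained during TEN-01-301 or TEN-01-302". It has the same sentence for vital signs. It leaves the baseline for continuous laboratory change undefined, and the SAP settles it as enrollment.

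Study 303 supplies no starting value of its own. Protocol 8.1 opens with "The following procedures will be conducted at Visit 1" and then lists consent, eligibility and dispensing only. Laboratory tests and ECG are scheduled once, at the final visit (Visit 3 for subjects from 302, Visit 4 for subjects from 301) or at early termination. Neither document plans change or shift from a value defined as pre-tenapanor.

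**The concern.** The objective in SAP 2.1 is safety "when administered twice daily (BID) for up to 52 weeks". Treatment in 303 lasts at most 39 weeks, so 52 weeks is reached only by counting parent-study exposure, and the sample size statement (SAP 3.1) does count it. SAP 3.7 then says: "Safety assessments will be based on the incidence, severity, and type of adverse events, and clinically significant changes" in laboratory tests, vital signs, ECG and physical examinations.

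The change tables do not follow the same clock. A subject in Cohort 4 whose laboratory value went from normal to high on tenapanor during 302 and stayed high would be tabulated as high at both ends, not as a shift. A mean effect that had levelled off before enrollment would give a change near zero. A reader of the study report could take such tables as showing no change over a year of treatment when they span 26 or 39 weeks.

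**Working it through.** **Inputs.** Weeks by cohort come from the SAP 3.6 table, "Treatment Cohorts for Summary Tabulations". The final-visit windows (Week 26 ± 2 and Week 39 ± 2) come from the schedule of assessments. Working assumption: the last parent-study value was taken at the end of the parent study.

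**Plan's own figure.** The Protocol Summary gives total tenapanor exposure of about 52 to 55 weeks. Cohort 1: 12 + 4 + 39 = 55. Cohort 4: 26 + 26 = 52. The range is reproduced by these two cohorts and by no other.

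**Tenapanor weeks before and after the starting value.** Share before = before ÷ (before + after).

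| Cohort | Before | After | Total | Share before | State at starting value |
|---|---|---|---|---|---|
| 1 | 16 | 39 | 55 | 16/55 = 29% | on drug |
| 2 | 12 | 39 | 51, interrupted | 12/51 = 24% | off drug, after 4 placebo weeks |
| 3 | 4 | 39 | 43 | 4/43 = 9% | on drug |
| 4 | 26 | 26 | 52 | 26/52 = 50% | on drug |
| 5 | 0 | 26 | 26 | 0% | tenapanor-naive |

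Only Cohorts 1 and 4 reach 52 nominal, uninterrupted weeks. Their within-subject change covers 39/55 = 71% and 26/52 = 50% of their time on drug.

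**Sensitivity to the final-visit window.** Cohort 1: 16/57 to 16/53 = 28% to 30%. Cohort 4: 26/54 to 26/50 = 48% to 52%.

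**Sensitivity to the timing of the last value.** If Cohort 1's last value came from the end of the 12-week period, 12/55 = 22% of drug time precedes it and 43/55 = 78% is covered. For a given test the gap closes fully only if its last parent-study measurement preceded the first tenapanor dose, which the documents neither state nor exclude.

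**What the planned tables already show.**
- Cohort 5: within-subject change over weeks 0 to 26 on drug, from a tenapanor-naive value.
- Cohort 3: change covering 39/43 = 91% of its drug time.
- Cohort 4 against Cohort 5, actual values at enrollment: 26 weeks of tenapanor against 26 weeks of placebo, among completers who rolled over. Within 301 there is no such contrast, because Cohorts 1, 2 and 3 have by then had 16, 12 and 4 weeks of tenapanor.
- Independent of the baseline: counts of clinically significant laboratory abnormalities, ECG normal/abnormal counts, and listings.

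**The case against.** The strongest reply is that the plan, read by cohort, does not lose the early period. Cohort 5 supplies within-subject change over weeks 0 to 26 and Cohort 4 continues over weeks 26 to 52, so the two together span 52 weeks, in different subjects. An effect that levels off between weeks 4 and 26 should be visible in Cohorts 3 and 5. This stands, and it limits the point to the tables for particular cohorts. It does not supply change over 52 weeks in the same subjects.

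A second reply is that change from enrollment suits a SAP written around the 303 period: adverse events count from the first dose of study drug, and the top exposure category is simply more than 26 weeks. Whether anything moves further on continued treatment is a fair question, which is why the existing tables should stay. But the stated objective reaches 52 weeks. The separate plan foreseen in SAP 2.1 is for other objectives or a changed use of the data, not for this one.

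Third, clinical significance of laboratory values is the investigator's judgement on each abnormal value and needs no baseline. That is correct, and those counts are unaffected.

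Fourth, SAP 3.6.2 already summarizes body weight from the parent studies by cohort. If that is a pre-drug value, cohort means can be compared for this one variable, though not as within-subject change.

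A reader might also infer that the proposed pre/post change would be better evidence than Cohort 4 against Cohort 5 at enrollment. The documents do not support that: the cohort contrast has a concurrent placebo group, and the pre/post change has no control.

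**Conclusion.** The point holds as a partial gap. If the last parent-study value was taken at the end of the parent study, the change and shift tables for Cohorts 1 and 4 leave out the first 16 of 55 and 26 of 52 weeks on tenapanor, and no planned table shows within-subject change over 52 weeks. It is a worthwhile, inexpensive improvement to a descriptive analysis; no test or power figure is affected.

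Three stronger readings are tempting and should be avoided:
- That the plan hides early effects. Cohorts 3 and 5, the actual values by cohort and the baseline-free counts show otherwise.
- That 29% and 50% measure bias. They are shares of time on drug. Cohort sizes and effect sizes are not given, so no distortion of the Overall column can be estimated.
- That the roughly 150 subjects with at least 52 weeks are Cohorts 1 and 4. That fits the nominal schedule, but the sample size section assigns no subjects to cohorts.

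The parent-study visit schedules are not in these documents, so confidence is moderate.

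**What to change.** Keep every change-from-enrollment table. In SAP 3.7.2 and 3.7.3 add, where parent-study data exist:
- supplementary by-cohort change tables for laboratory tests, vital signs and ECG, and laboratory shift tables, starting from the last value before the subject's first tenapanor dose;
- at least Cohorts 1 and 4, using the parent-study baseline. Cohort 2 would use the same baseline, and Cohort 3 its last 301 value before tenapanor, if available. Cohort 5 is unchanged, since its enrollment value already qualifies;
- a footnote on Cohort 2's 4-week placebo gap;
- a footnote that the existing Overall column mixes on-drug, off-drug and tenapanor-naive starting values;
- a statement that the pre/post change is uncontrolled.

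The cost is SAP wording, one derived baseline variable and extra descriptive tables. No new 303 procedure is needed. The SAP already brings in parent-study data, and Protocol Section 10 lets the SAP change the statistical considerations without a protocol amendment. The downside is dependence on laboratory tests, vital signs and ECG having been collected at parent baseline, which these documents do not show; a test without such a value would keep only its change from enrollment.
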